#### 4.7.1.3.2. Upper Arm Functional Assessments

- Performance of upper limb (PUL) – Middle level elbow dimension score
  - Sum of the 9 items for this particular dimension (Maximum = 34). These include: “Hand(s) to Mouth”, “Hand(s) to table from lap”, “Move weight on table”, “Lifting light cans”, “Lifting heavy cans”, “Stacking light cans”, “Stacking heavy cans”, “Remove lid from container”, and “Tearing paper”.
  - Time to lift 5 light cans (sec.)
  - Time to stack 5 light cans (sec.)
  - Time to lift 5 heavy cans (sec.)
  - Time to stack 5 heavy cans (sec.)
  - Composite (or average) time to complete the following tasks: lift 5 light cans, lift 5 heavy cans, stack 5 light cans, and stack 5 heavy cans.
- a. Note that when deriving the average time to complete the selected tasks listed above, one or more of the times may be missing for a given patient at one or more time points. If such a scenario occurs, the average of the “non-missing” times should then be determined. For example, if the “Time to lift 5 light cans (sec.)” is missing for a patient at a particular time point (s), and the other 3 quantities are non-missing, then the average time to complete the selected tasks should be computed off of the 3 non-missing quantities.
- PUL high level/shoulder dimension (patients receiving ACE-083 in the BB muscle during the Part 2 open-label phase)
  - Shoulder domain score which represents the sum of the following 4 items that the patient is asked to do on the preferred side [either right or left side identified by patient to be done on the same side for all scheduled times]:
    - a. Largest weight patient can use to perform shoulder abduction to shoulder height (elbow to shoulder level)
    - b. Largest weight patient can use to perform shoulder abduction above shoulder height (elbow to eye level)
    - c. Largest weight patient can use to perform shoulder flexion to shoulder height (elbow to shoulder level)
    - d. Largest weight patient can use to perform shoulder flexion above shoulder height (elbow to eye level)

Each of the 4 components above is scored depending on the highest weight performed where scores are: 0 = Unable; 1 = Able no weights; 2 = 200 g; 3 = 500 g; 4 = 1000 g. The maximum score is 16.

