**4.1.4. Definitions of Baseline****Part 1 and Part 2 (Double-blind phase)**

For MRI, PD, and safety data, baseline is defined as the last non-missing assessment prior to the first dose of study drug administration. Theoretically, this is the Day 1 pre-dose assessment. For patients that are randomized (applicable to patients participating in Part 2) but do not receive any study drug administration, the date of randomization will be the baseline reference.

For motor function data (lower leg and upper arm functional assessments), strength (QMT by handheld device), gait, and FSHD-HI data whose pre-treatment assessments are performed up to three times prior to the first dose, the baseline is defined as the average of the non-missing values. Theoretically, this would be at the Screening Day -28, Screening Day -7, and Day 1 visits. The first dose date will serve as the reference from which the non-missing pre-treatment values would be identified. For patients that are randomized (applicable to patients participating in Part 2) but do not receive any study drug administration, the date of randomization will be the baseline reference. The last non-missing assessment prior to the first dose of study drug administration will also be determined for this data and will be available for sensitivity analyses for any analyses of changes from baseline as appropriate.

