Additional techniques for handling missing data may also be considered and evaluated.

- If a patient has a Day 190 assessment performed after having received the Day 190 dose (first dose in the open-label phase), then the Day 190 assessment for that patient will be included in statistical analyses of Day 190 data only if the difference between the Day 190 assessment and the Day 190 dose date is less than or equal to 7 days.
- Descriptive statistics for quantitative parameters will be provided using number of observations (N), mean, standard deviation (SD), standard error of the mean (SEM), median, minimum and maximum;
- Should it be necessary to convert duration in days to duration in months, the duration in days will be divided by 30.417 (365/12) to calculate duration in months.
- Descriptive statistics for qualitative parameters will be provided using frequencies (N) and percentages (%).
- If the result of a continuous variable contains nonnumeric values (e.g. ‘<X’ or ‘>X’), the imputed values used for the descriptive statistics will be determined by considering the following rules:
  - If the value is ‘<X’, the value used will be X/2;
  - If the value is ‘>X’, the value used will be X.
- Concerning the determination of absolute and percent change from baseline for data such as MRI and muscle strength where assessments are reported separately for the left and right sides and the average absolute and/or percent change from baseline is needed, the absolute and/or percent change is determined for the left and right sides separately and then averaged. The “average” represents the “average” absolute (or percent) change from baseline for the left and right sides. For MRI and muscle strength data, should a patient have an MRI and/or strength assessment on one side (i.e. right side) but not the other side at an individual timepoint, the value for the average absolute (or percent) change from baseline for that patient and timepoint will be the absolute (or percent) change from the side from which the MRI and/or strength assessment was obtained.

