#### **Motor Function (Upper Arm): Performance of Upper Limb (PUL) [Middle Level Elbow Dimension] – (BB Muscle Group)**

Individual data will be listed.

Descriptive statistics will be provided by treatment group for those receiving study drug in the biceps brachii muscle for the following components from the mid-level PUL:

- Composite (or average) of time to complete the four timed tasks from the mid-level PUL
- Time to lift 5 light cans
- Time to stack 5 light cans
- Time to lift 5 heavy cans
- Time to stack 5 heavy cans
- Mid-level elbow dimension total score

For the composite (or average) of times to complete the four timed tasks from the mid-level PUL, an ANCOVA model will be fitted in order to assess the effect of ACE-083 on the Day 190 percent change from baseline data. Covariates to be included in the model are TREATMENT, MRC-MMT GRADE CATEGORY, and BASELINE where BASELINE represents the baseline

PUL composite time and each of the other covariates are defined the same as what was done for the primary analysis.

The effect of ACE-083 on the Day 190 percent change in the mid-level PUL composite time from baseline versus placebo will be estimated using the ANCOVA model described above and tested using a 0.1 significance level (2-sided). The least-squares mean estimate along with the corresponding 90% confidence interval will be provided. In addition, the 95% confidence interval will also be provided as well as a bar chart of the least squares mean estimates ( $\pm$  SEM) for each of the treatment groups.

A mixed model repeated measures (MMRM) analysis will be performed to assess the sensitivity to the ANCOVA analysis described above. An unstructured covariance structure will be used to model the within-patient covariance across visits. Other covariance structures will be considered if the unstructured covariance fails. The covariates to be included consist of all of the covariates described above for the ANCOVA with the addition of the following additional covariates: VISIT where VISIT represents the scheduled visit day post first dose of MRI assessment and TREATMENT\*VISIT.

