For both the ANCOVA and MMRM analyses, multiple imputations will be performed for missing data. Twenty imputations will be performed. The seed to be used is specified in [Section 6](#). The assumption of the missing data mechanism will be missing at random (MAR) unless the data suggest otherwise. The missing data pattern (monotone or arbitrary) will also be evaluated and the regression method for imputing missing data will be utilized for each scheduled timepoint with missing data. Covariates to be included when imputing missing data include: MRC-MMT GRADE CATEGORY, TREATMENT, BASELINE, and PUL percent change data at scheduled timepoints prior to the timepoint at which PUL percent change is being imputed.

The table below illustrates the covariates that should be used for imputing missing data for selected timepoints:

Data to be imputed	Covariates to use in multiple imputation regression model
Baseline PUL	MRC-MMT GRADE CATEGORY, TREATMENT
Day 22 percent change in PUL from baseline	MRC-MMT GRADE CATEGORY, TREATMENT, BASELINE
Day 43 percent change in PUL from baseline	MRC-MMT GRADE CATEGORY, TREATMENT, BASELINE, Day 22 PUL percent change
Day 190 Percent change in PUL from baseline	MRC-MMT GRADE CATEGORY, TREATMENT, BASELINE, Days 22, 43, 64, 85, 106, 148, and 169 PUL percent change from baseline

Note: PUL means either the composite (mean) time to perform the 4 timed activities or the PUL mid-level dimension score.

Analysis findings will be presented for Day 190 percent change data where missing data is not imputed (observed data) as well as for Day 190 percent change data where multiple imputations are performed for missing data to assess the impact of the missing data on the observed study data. The analyses where multiple imputations are performed are considered to be primary.

The analyses described above will also be performed for the mid-level PUL dimension score.

The Per Protocol Set will be used for the primary analysis. The analyses described above will also be repeated for the Full Analysis Set.

Additional analyses may be performed as appropriate.

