#### **Selected Motor Function, FSHD-HI Arm/Shoulder Function Subscale Score, MVIC, MRC-MMT Score, FSHD-HI Mobility and Ambulation Subscale Score**

For mid-level PUL composite time (BB patients only), 6MWD (TA patients only), time to complete the 10mW/R (TA patients only), 4-stair climb ascend time (TA patients only), 4-stair descend time (TA patients only), FSHD-HI arm/shoulder function subscale score (BB patients only), FSHD-HI mobility and ambulation subscale score (TA patients only), MVIC (elbow flexion – BB patients), MVIC (ankle dorsiflexion – TA patients), MRC-MMT score (elbow flexion – BB patients), MRC-MMT score (ankle dorsiflexion – TA patients), descriptive statistics will be provided for the Placebo □ ACE-083 treatment sequence for the difference in percent (or absolute) change observed between Day 190 and pre-first treatment baseline (1st 6 months) and the percent (or absolute) change observed between Day 358 and the open-label treatment baseline (2nd 6 months).

In addition, the effect of ACE-083 administered during the open-label extension compared to the treatment administered in the double-blind placebo-controlled phase will be examined for those receiving ACE-083 during the double-blind phase and separately for those receiving placebo during the double-blind phase by comparing the percent (or absolute) change observed between

Day 190 and pre-first treatment baseline (1st 6 months) and Day 358 versus open-label treatment baseline (2nd 6 months) using an ANCOVA model for each individual data parameter.

Covariates to be included into the model are SEQUENCE, MRC-MMT GRADE CATEGORY, HEIGHT (only for 6MWD and 10mW/R) and BASELINE where:

- SEQUENCE refers to the treatment sequence from double-blind to open-label (ACE-083 □ ACE-083 or Placebo □ ACE-083)
- MRC-MMT GRADE CATEGORY refers to the randomization stratification factor from the double-blind phase
- BASELINE refers to baseline from the double-blind phase
- HEIGHT refers to the patient's height (cm)

Least squares estimates for each sequence and 90% confidence intervals will be provided and will be tested using a 0.1 significance level (2-sided).

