#### 4.7.2.5. Other Analyses

The number and percentage of patients belonging to each of the following criteria will be summarized by treatment group:

- Day 190 percent change in TMV from baseline  $\geq 10\%$
- Day 190 percent change in 6MWD from baseline  $\geq 10\%$
- Day 190 absolute change in 6MWD from baseline  $\geq 30$  m
- Day 190 percent change in time to complete 10mW/R from baseline  $\geq 10\%$
- Day 190 absolute change in time to complete 10mW/R from baseline  $\geq 0.5$  sec.
- Day 190 percent change in 4-stair ascend time from baseline  $\geq 10\%$
- Day 190 percent change in PUL composite (mean) time to perform 4 timed activities from baseline  $\geq 10\%$
- Day 190 absolute change in FSHD-HI total score from baseline  $\leq -8$
- Day 190 absolute change in FSHD-HI arm/shoulder sub-score from baseline  $\leq -8$  (BB patients only)
- Day 190 absolute change in FSHD-HI mobility sub-score from baseline  $\leq -8$  (TA patients only)
- Day 190 absolute change in FSHD-HI activity limitation sub-score from baseline  $\leq -8$

For each criterion listed above, Fisher's exact test will be used to compare the proportions of patients belonging to the individual criterion between the two treatment groups using a 0.1 significance level.

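### The mid-level PUL composite time averages whichever can-task times are present at each visit, so a change in which tasks were timed can appear as a change in performance.

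*SAP*

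**What the plan says.** SAP 4.7.1.3.2 lists four timed tasks (lifting and stacking five light cans, and the same with heavy cans) and averages them into a composite. It foresees that "one or more of the times may be missing for a given patient at one or more time points" and says the remaining times are then averaged; for one missing light-can time, "then the average time to complete the selected tasks should be computed off of the 3 non-missing quantities". It sets no minimum number of tasks and no common task set across visits.

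Under SAP 4.1.4, "the baseline is defined as the average of the non-missing values" for motor function data, taken over up to three pre-dose assessments. The only consistency rule for baseline PUL, in SAP 4.1.5, concerns the preferred side, not the task.

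The composite is used as follows:

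- **Day 190 comparison (SAP 4.7.2.2, mid-level PUL).** For the composite, "an ANCOVA model will be fitted in order to assess the effect of ACE-083 on the Day 190 percent change from baseline data", tested at two-sided 0.1, with an MMRM as sensitivity analysis.
- **Imputation (same section).** The note to the table reads: "PUL means either the composite (mean) time to perform the 4 timed activities or the PUL mid-level dimension score". Single task times are not imputed.
- **Other uses.** The composite enters the open-label comparison (SAP 4.7.2.3), the subgroup analyses (4.7.2.4) and a 10% criterion in 4.7.2.5 based on the "percent change in PUL composite (mean) time to perform 4 timed activities from baseline".

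MRI and strength are handled differently. SAP 4.1.5 takes the change for each side first. If one side was not assessed, the patient's value "will be the absolute (or percent) change from the side from which the MRI and/or strength assessment was obtained", so baseline and visit refer to the same side.

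**The concern.** A percent change compares like with like only if numerator and denominator rest on the same tasks. Under the available-task rule, a patient with four tasks at baseline and three at Day 190 is compared on two different averages. If the tasks differ in duration, losing a slow one shortens the composite and losing a fast one lengthens it, with no change in the patient. A composite built from one to three tasks is treated as observed, so the multiple imputation does not repair it.

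The composite is an SAP-defined BB measure supporting the secondary motor-function objective. If times go missing for reasons unrelated to arm, the cost is mainly extra variance in a comparison with 12 to 14 patients per arm. If tasks are lost or gained differently by arm, for example because inability is stored as a missing time, the treatment comparison itself can be biased, and losing a slower task would look like improvement. The available text does not show how inability is recorded; the PUL form in Protocol Appendix 4 is not in the copy reviewed. Bias is therefore a possibility, not an established fact.

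**Working it through.** The plan gives no figure to reproduce here, so the check is algebra on its own definition.

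**Inputs.** From SAP 4.7.1.3.2: four tasks, unweighted mean, missing times dropped. Assumed, because the documents give no task times: each light-can task takes 1 unit and each heavy-can task r units, with r = 1.25 to 2 as the working range. Every task time is held equal at baseline and Day 190, so any non-zero result is task mix alone.

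**Formulas.** Full composite: F = (2 + 2r)/4 = (1 + r)/2.

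- One heavy time missing at Day 190: [(2 + r)/3]/F − 1 = (1 − r)/[3(1 + r)].
- One light time missing: the same size with opposite sign.
- Both heavy times missing: 1/F − 1 = (1 − r)/(1 + r).

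| r | One heavy missing | One light missing | Both heavy missing |
|---|---|---|---|
| 0.8 | +3.7% | −3.7% | +11.1% |
| 1 | 0 | 0 | 0 |
| 1.25 | −3.7% | +3.7% | −11.1% |
| 1.5 | −6.7% | +6.7% | −20.0% |
| 2 | −11.1% | +11.1% | −33.3% |

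**10% criterion.** Setting (r − 1)/[3(1 + r)] = 0.10 gives r = 1.3/0.7 = 1.86. Below that ratio, one missing task alone does not produce a 10% shift.

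**Gaps at baseline.** One heavy time absent at one of three pre-dose assessments gives a baseline of [2F + (2 + r)/3]/3. With all four tasks timed at Day 190, the spurious change is +1.3% (r = 1.25) to +3.8% (r = 2).

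**Missing times unrelated to arm.** Assume a fraction q of patients miss one task chosen at random from the four. The mean shift is zero and the added variance is q·s², with s = 3.70 (r = 1.25) to 11.11 (r = 2) points.

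- q = 10%: added SD 1.17 to 3.51 points.
- q = 20%: added SD 1.66 to 4.97 points.

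The SAP gives no SD for PUL. Against an illustrative 9% (its figure for muscle volume and 6MWD), the variance rises by between 0.1 × 3.70²/81 = 1.7% and 0.2 × 11.11²/81 = 30%.

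**Missing times that differ by arm.** Each extra patient in one arm who loses one heavy time moves that arm's mean by 3.70/14 = 0.26 to 11.11/12 = 0.93 points.

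**A real change can be masked.** Suppose every task is 10% slower and one heavy time is missing at Day 190. The SAP rule gives 1.1 × (1 − 0.037) − 1 = +5.9% at r = 1.25 and 1.1 × (1 − 0.111) − 1 = −2.2% at r = 2, where the sign reverses. Using only the tasks timed at both visits gives +10% in each case.

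**The case against.** The size rests on assumptions. Task ratio, missing rate and PUL SD are all unknown, and the model treats lifting and stacking as equally long. The 30% variance increase joins the top of both assumed ranges to a borrowed SD; with an assumed SD of 20%, the same worst case adds 24.7/400, about 6%. One light and one heavy time missing together cancel exactly. All of this stands, and it limits what can be said about size. It does not alter the rule.

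Missing times may be rare. Exclusion criterion 2 (Protocol 8.2) removes patients whose comorbidities would limit functional testing, and for patients eligible for both muscles, ability to complete assessments helps decide which is treated (Protocol 10.1). Neither guarantees complete times, and the SAP itself expects gaps.

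Safeguards exist. The mid-level dimension score includes the four can items and gets the same Day 190 analyses, and each task time is summarised by arm. These help to show lost tasks but do not correct the composite. The open-label, subgroup and 10% analyses list the composite without the score.

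The 10% criterion is written as an increase of at least 10%. Read literally for a time, shortening from a lost heavy task would not meet it. That is fair; the 1.86 threshold speaks to size, not direction.

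Matching is not always closer to the complete-data answer. If light tasks stay at 1 and heavy tasks fall from 2 to 1, the complete-data change is −33.3%. The SAP rule still gives −33.3% with one time missing, while matching gives −25.0% (heavy missing) or −40.0% (light missing). This stands: matching is exact only when tasks change in proportion.

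Finally, Protocol 14.2.3.2 plans muscle function to be described, with other analyses only as appropriate. The ANCOVA is an SAP addition on a measure that is not primary. That bears on priority, not on whether the derivation is sound.

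**Conclusion.** The concern holds. The SAP states a rule that can give a wrong percent change whenever the set of timed tasks differs between baseline and Day 190, and it has no counterpart to the matching it uses for MRI and strength. With performance unchanged and r between 1.25 and 2, one time missing at Day 190 shifts that patient's result by 3.7 to 11.1 points; losing both heavy times gives 11.1% to 33.3% spurious shortening. The effect vanishes at r = 1 and reverses below it. The actual effect on the trial cannot be set from the documents: it is mainly noise if missing times are unrelated to arm, and possibly bias if they are not. The primary total muscle volume analysis is unaffected. This is worth correcting because the remedy is cheap; confidence is medium because the frequency of missing times and the recording of inability are unknown.

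**What to change.** For each post-baseline visit, define percent change as the mean task time at that visit divided by the mean baseline time, minus 1, with both means over only the tasks timed at baseline and at that visit. Average each task's baseline across the pre-dose assessments first. When all times are present this equals the SAP's composite change, because averaging over tasks and then assessments gives the same mean as the reverse order.

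Also specify the following:

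- Keep one BASELINE covariate in the ANCOVA, MMRM and imputation models: the mean of the per-task baselines available for that patient. It is fixed before randomisation.
- Send patients with no common task to the existing multiple imputation.
- Report the current available-task version as a sensitivity analysis.
- Tabulate which tasks were timed, by arm and visit, and read the result beside the mid-level dimension score.
- State how a task that the patient could not complete is recorded.

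**Cost.** SAP wording, one revised derivation, one sensitivity run and one table. No new data are needed, since the four times are already SAP variables.

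**Limits.** Patients with fewer common tasks have noisier values, the common set can differ between visits, and lost or gained ability is not captured. The repair is approximate when tasks change unequally. For example, let light tasks go from 1 to 0.8 and heavy tasks stay at 2, a complete-data change of 1.4/1.5 − 1 = −6.7%. With one heavy time missing, the SAP rule gives 1.2/1.5 − 1 = −20.0% and matching gives 1.2/1.333 − 1 = −10.0%. With one light time missing, they give 1.6/1.5 − 1 = +6.7% and 1.6/1.667 − 1 = −4.0%.

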#### 4.7.1.4. Patient Reported Outcome Variables

- Total Facioscapulohumeral Disease Health Index (FSHD-HI) score
- The 14 subscale scores of the FSHD-HI survey
  - Shoulder and Arm Function, Mobility and Ambulation, Fatigue, Cognitive Function, Activity Limitation, Core Strength and Function, Gastrointestinal Function, Social Performance, Body Image, Hand and Finger Function, Social Satisfaction, Pain, Emotional Health, and Communication

#### 4.7.2. Analyses

##### 4.7.2.1. Part 1

Unless otherwise specified, no imputations for missing data will be performed for Part 1 data.

##### MRI and Muscle Strength Variables

###### Unilateral Cohorts

Individual MRI and strength data will be listed.

For each MRI and strength variable, the raw data as well as the absolute and percent change from baseline in the treated TA or BB muscle, untreated TA or BB muscle, and the treated minus untreated TA or BB muscle will be summarized for each scheduled time point.

Least square mean estimates of the effect of ACE-083 and corresponding 90% and 95% confidence intervals will be produced using an analysis of covariance (ANCOVA) for the following variables: TMV percent change from baseline 3 weeks post last dose, CCMV percent change from baseline 3 weeks post last dose, FF absolute change from baseline 3 weeks post last dose, percent change in elbow flexion MVIC 3 weeks post last dose (BB cohorts), and percent change in ankle dorsiflexion MVIC 3 weeks post last dose (TA cohorts).

The ANCOVA model will contain the following covariates:

- COHORT represents the dose level of ACE-083 administered to the muscle.
- BASELINE represents the baseline value of the parameter of interest
- BASELINE\*COHORT represents the interaction of the baseline and cohort

The analysis described above will be performed for the treated side as well as for the difference in treated and untreated sides and will be done separately for the TA and BB cohorts.

For BB patients, the above analyses will be repeated using the patient's "preferred" side used for the PUL test for patients.

Additional analyses may be performed as appropriate.

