8. STUDY POPULATION

8.1. Inclusion Criteria

Patients are eligible to be included in the study only if they meet all of the following criteria at screening:

Inclusion Criteria:

1. Age \geq 18 years
2. Genetically-confirmed FSHD1 or FSHD2 (or a first-degree relative with genetically confirmed FSHD1 or FSHD2) and clinical findings meeting FSHD criteria
3. Part 1 TA cohorts:
 - a. 6-minute walk distance \geq 150 meters (without a brace)
 - b. Left and/or right ankle dorsiflexion Medical Research Council (MRC) manual muscle testing (MMT) grade 3 to 4+, inclusive ([Appendix 3](#))

Note: Contralateral side may be MRC MMT grade 3 to 5

Part 1 BB cohorts:

- a. Left and/or right elbow flexion MRC MMT grade 3 to 4+, inclusive ([Appendix 3](#))

Note: Contralateral side may be any MRC MMT grade

Part 2 TA cohorts:

- a. 6MWD \geq 150 and \leq 500 meters (without a brace); a maximum of 20% of enrolled patients with 6MWD \geq 450 meters will be included
- b. Left and right ankle dorsiflexion MRCMMT grade 3 to 4+, inclusive ([Appendix 3](#))

Part 2 BB cohorts:

- a. Left and right elbow flexion MRC MMT grade 3 to 4+, inclusive ([Appendix 3](#))
4. Females of childbearing potential (defined as sexually mature women who have not undergone hysterectomy or bilateral oophorectomy, or are not naturally postmenopausal \geq 24 consecutive months) must have negative urine pregnancy test prior to enrollment and use highly effective birth control methods (abstinence, oral contraceptives, barrier method with spermicide, or surgical sterilization) during study participation and for 8 weeks following the last dose of ACE-083. Hormonal birth control use must be stable for at least 14 days prior to Day 1. Males must agree to use a condom during any sexual contact with females of childbearing potential while participating in the study and for 8 weeks following the last dose of ACE-083, even if he has undergone a successful vasectomy. Patients must be counseled concerning measures to be used to prevent pregnancy prior to the first dose of ACE-083.

5. Ability to adhere to the study visit schedule/procedures, and to understand and comply with protocol requirements
6. Signed written informed consent

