10. TREATMENT OF PATIENTS

10.1. Treatments Administered

Using electromyography (EMG) or ultrasound guidance, each dose of study drug will be administered into the non-tendinous portion of the TA or BB as a series of up to 5 equal-volume injections. The use of EMG or ultrasound guidance will ensure that viable muscle is present at the injection site. If the degree of atrophy or fibro-fatty infiltration poses administration challenges, injections of ACE-083 should be distributed at least 2 cm apart into viable muscle. Injection site locations as well as measures to avoid adjacent nerves and blood vessels and prevent intravascular injection are outlined in the Investigational Product (IP) Handling Guide.

For unilateral dosing, if disease involvement in the lower leg or upper arm is asymmetric, the side that is weakest should be injected provided the MRC criterion is met. For bilateral dosing in Part 1, if only one side is weak (i.e., contralateral side is MRC grade 5), it is acceptable to enroll the patient and to inject only the weak side. If a patient meets inclusion criteria for both the TA and BB, the investigator will choose one target muscle based on the patient's clinical presentation as well as on cohort availability and ability to complete assessments for muscle volume (MRI), strength, and function.

In Part 1, Cohorts 1 and 2, each dose will be administered unilaterally into the same targeted muscle, once every 3 weeks for up to 5 doses. For optional Cohort 3, bilateral dosing may be explored (determined by SRT), with a maximum absolute dose level of 250 mg/muscle administered bilaterally, every 3 weeks for 5 doses.

For Part 2, ACE-083 or placebo (normal saline) will be administered every 3 weeks for approximately 6 months (9 doses). Patients who complete the double-blind treatment period will immediately roll over to open-label treatment of ACE-083, receiving the same dose of active drug, bilaterally in either the TA or BB muscle, once every three weeks for approximately 6 months (8 doses).

The planned dose scheme for Part 1 and 2 is shown below.

Table 4: Cohort Schedule for Study A083-02**Part 1: N= Up to 36 (3-month, dose-escalation, non-randomized, open-label)**

Cohort	Muscle	Dose Level ^a	ACE-083 n
1a	Tibialis anterior	150 mg	6
2a	Tibialis anterior	200 mg ^b	6
3a (optional)	Tibialis anterior	TBD ^b	6

Cohort	Muscle	Dose Level ^a	ACE-083 n
1b	Biceps brachii	150 mg	6
2b	Biceps brachii	200 mg ^b	6
3b (optional)	Biceps brachii	TBD ^b	6

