## Part 1 – Biceps Brachii

ACE-083 150 mg Unilateral	ACE-083 200 mg Unilateral	ACE-083 240 mg Unilateral	Overall
------------------------------	------------------------------	------------------------------	---------

Listings will contain only the treatment groups shown with no “Overall” group.

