### Unilateral vs. Bilateral (Part 1)

In Part 1 of this study, patients may be treated unilaterally (meaning that the patient receives his/her dose either on the left TA or BB muscle or the right TA or BB muscle) or bilaterally (meaning that the patient receives his/her dose on both the right and left sides).

For patients receiving ACE-083 unilaterally, the side treated will vary from patient to patient within a cohort. To properly identify the side treated, the dataset(s) that identify the dose administrations for the individual patient will be used.

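### The SAP repeats the Part 1 biceps estimates of the ACE-083 effect on the PUL-preferred arm, but dosing was unilateral and nothing requires that arm to be the injected one

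*SAP*

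**What the plan says.** SAP 4.7.2.1, under Unilateral Cohorts, plans ANCOVAs with COHORT, BASELINE and their interaction, and presents the least-squares means as estimates of the ACE-083 effect with 90% and 95% intervals. For BB patients the outcomes are percent change in total muscle volume, percent change in calculated contractile muscle volume, absolute change in fat fraction, and percent change in elbow flexion MVIC, all three weeks after the last dose. COHORT is defined as the dose that the muscle was given. "The analysis described above will be performed for the treated side as well as for the difference in treated and untreated sides", with TA and BB handled apart. Then comes the sentence at issue: "For BB patients, the above analyses will be repeated using the" side the patient prefers for the PUL.

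SAP Table 1 and section 4.1.3 make every BB cohort unilateral, at 150 mg, 200 mg and, for Cohort 3b, "ACE-083 240 mg Unilateral". On the choice of arm, Protocol 10.1 says that for unilateral dosing, where involvement is asymmetric, "the side that is weakest should be injected provided the MRC criterion is met". Protocol 8.1 says of the other arm in Part 1 BB patients: "Contralateral side may be any MRC MMT grade". SAP section 6 adds that "the side treated will vary from patient to patient within a cohort" and that it is to be read from the dosing data.

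**The concern.** In a unilateral cohort every patient has one injected and one uninjected arm, so an analysis on the preferred arm estimates a drug effect only in patients whose preferred arm was injected. The SAP neither restricts the repeat to those patients nor asks how many there are. If it is programmed as written, an uninjected biceps is entered under COHORT as 150, 200 or 240 mg, which contradicts the SAP's own definition of COHORT, and the output is labelled an ACE-083 effect.

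What is at stake is small but concrete: a supplementary table could understate the effect. If mismatches fall unevenly across cohorts of six, it could also suggest a dose pattern that reflects arm preference and not dose.

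**Working it through.** **1. Number of patients.** SAP Table 1 plans 6 + 6 + 6 = 18 BB patients in Part 1, which matches its stated total, and all are unilateral. The protocol left Cohort 3 open to bilateral dosing, but the SAP fixes 3b as unilateral. So 18 of 18 have an uninjected arm, and the number whose preferred arm is the uninjected one can be anything from 0 to 18.

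**2. Is there a link between preferred and injected arm?**
- Injected arm: the weakest qualifying side if involvement is asymmetric (Protocol 10.1); it varies by patient (SAP section 6).
- Preferred arm: SAP 4.1.5 restricts baseline PUL to the patient's preferred side and does not mention treatment. SAP 4.7.1.3.2 says the patient identifies the side, but only for the shoulder dimension used in the Part 2 open-label phase.
- Neither document states that the two arms must coincide.

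**3. Rough size of the dilution.** Let f be the fraction of patients whose preferred arm was not injected and D the effect in an injected arm. Assume no change in the uninjected arm. The raw mean on the preferred arm is then (1 − f) × D. The documents do not give f. D = 10 percentage points is borrowed for illustration from the Part 2 sample-size section.

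| f (assumed) | (1 − f) × 10 |
|---|---|
| 0 | 10 |
| 0.25 | 7.5 |
| 0.5 | 5 |
| 0.75 | 2.5 |
| 1 | 0 |

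**4. Chance of at least one mismatch.** If each patient mismatches independently with probability f, this is 1 − (1 − f)^n. At f = 0.25 it is 1 − 0.75^6 = 82% in a cohort of 6 and 1 − 0.75^18 = 99.4% across 18. At f = 0.10 it is 1 − 0.9^6 = 47% and 1 − 0.9^18 = 85%. At f = 0 it is zero.

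**5. Uneven mismatch across doses.** Suppose the effect is 10 in every cohort and 0, 1 and 3 of 6 patients mismatch. The raw preferred-arm means are 10, 10 × 5/6 = 8.3, and 10 × 3/6 = 5. That looks like a dose pattern where there is none.

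**6. The contrast.** The analyses to be repeated include treated minus untreated. That contrast uses both arms and is fixed by the dosing record, so the preferred side plays no part in it. The SAP defines no substitute.

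**7. Can the ANCOVA be fitted in matched patients only?** The mean model has 6 parameters: intercept, 2 for cohort, 1 for baseline, 2 for interaction. With 18 patients there are 18 − 6 = 12 residual degrees of freedom. At f = 0.5 about 9 patients remain, leaving 3. At f = 0.75 only 4 or 5 remain, fewer than the parameters. Each cohort also needs at least two matched patients with different baselines to support its own slope.

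**The case against.** The strongest defence is that the repeat is meant to pair MRI and strength with the arm that performs the PUL. That is a reasonable aim, but in a unilateral cohort it describes the tested arm and gives a drug effect only where that arm was injected.

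It can also be said that the rule for choosing the PUL arm in Part 1 is not visible. Part 1 uses the middle domain only, the available text of Protocol Appendix 4 has no more than its heading, and the Study Manual is not to hand. A rule matching the tested arm to the injected arm may exist there. This stands as a limit on how often the problem occurs. It does not repair the SAP sentence, which carries no such condition.

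Three stronger readings are tempting, and the documents do not support them.
- A reader might infer that all 18 patients are affected. Only those whose preferred arm was uninjected contribute the wrong muscle, and there may be none.
- A reader might infer that most patients prefer the stronger, uninjected arm. No document links arm strength to PUL preference, and the weakest-side rule applies only to asymmetric disease and only if the MRC criterion is met.
- A reader might infer that the treated-minus-untreated result changes sign. SAP 4.7.1.2 keeps the treated and untreated sides fixed for each patient, so it does not. A reversal would need a preferred-minus-other contrast, which the SAP never specifies.

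The (1 − f) factor is also only a guide. The planned model adjusts for baseline and its interaction with cohort, and baselines may differ between weaker and stronger arms, so the least-squares means need not shrink by exactly that factor.

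**Conclusion.** The sentence is wrong as written for the unilateral section, because it allows an uninjected muscle to be analysed as a dosed one and reported as an ACE-083 effect. The number of patients affected is unknown, between 0 and 18. Assuming no change in the uninjected arm, the supplementary estimate would be diluted to roughly (1 − f) of the effect, with f anywhere from 0 to 1. The preferred-side form of the treated-minus-untreated analysis is undefined.

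The importance is minor. The treated-side and treated-minus-untreated analyses stand. Part 1's primary objective is safety, it has no formal sample size, and no stated decision rule uses the preferred-arm result. The same sentence in Part 2 is sound in this respect, because dosing there is bilateral and either arm is injected.

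**What to change.** Delete the preferred-side sentence from the Unilateral Cohorts part of SAP 4.7.2.1 and leave it in Part 2.

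If the sponsor wants to keep it, limit it to BB patients whose PUL-preferred arm was the injected arm, report how many there are in each cohort, and summarise them descriptively or with a reduced model, since the six-parameter ANCOVA may not be estimable. Any summary that includes uninjected preferred arms should be split by whether the arms match and should not be called an ACE-083 effect. State that the treated-minus-untreated analysis has no preferred-side version.

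The cost is one SAP sentence and no new data, since the dosing datasets identify the injected side. The downside is that a supplementary analysis is dropped or rests on fewer patients.
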